3.4.3 Secondary outcomes

Incidence of the following outcomes up to 36 completed weeks post menstrual age unless specified otherwise:

- 1. Death
- 2. Death or brain injury
- 3. Major morbidity (see above for components of combined morbidity)
- 4. Death or major disability up to 3 years corrected age
- 5. Death up to 3 years corrected age
- 6. Major disability up to 3 years corrected age
- 7. Brain injury on ultrasound
- 8. IVH
 - I. IVH all grades

Page 26 of 81

- II. grades 3 and 4
- III. grade 4
- 9. Severe retinopathy defined as treatment for ROP or stage 4 ROP
- 10. Necrotizing enterocolitis
- 11. Late onset sepsis
- 12. Patent Ductus Arteriosis requiring treatment
- 13. Chronic lung disease (also known as bronchopulmonary dysplasia) defined as receiving supplemental oxygen or any form of assisted ventilation at 36 completed weeks post menstrual age for 4 consecutive hours in a 24 hour period

3.4.4 Descriptions of secondary outcomes – follow up

Assessment of death or major disability at follow up

Evaluation of major disability up to 3 years will be assessed by a short paediatric questionnaire that can be filled out from routine hospital assessments and the parent completed Ages and Stages questionnaire.²¹

Major disability is defined by a positive result on either:

(i) a Short Health Status Questionnaire completed by a qualified health professional documenting either: -

- (a) Cerebral palsy with an inability to walk unassisted at or after 2 years corrected age, or
- (b) Severe visual loss (legally blind i.e. corrected acuity <6/60 in both eyes), or
- (c) Deafness, requiring a hearing aid or cochlear implants
- (d) Major problems with language or speech at or after 2 years corrected for gestation, as defined by the inability to use more than 10 words (including signed words)^{22, 23}

(ii) parent report of a score indicative of delay on the Ages and Stages Questionnaire (ASQ). The ASQ assessment will be calibrated against the BSID III using data from a sample of up to 180 study participants. The results of the calibration study will be used to refine the ASQ's contribution to the major disability endpoint, i.e. it will inform the choice of ASQ score cut-point that will be used to define the relevant degree of developmental delay. This work will be conducted blinded to treatment and finalised prior to database release for final analysis.

3.4.5 Tertiary outcomes

- 1. birth weight
- 2. blood transfusions (number of transfusions up to 36 weeks corrected for gestation)
- 3. admission temperature
- 4. peak bilirubin in the first 7 days after birth
- 5. peak haematocrit in the first 7 days after birth
- 6. length of hospital admission (to discharge)
- 7. maternal postpartum haemorrhage requiring blood transfusion
- 8. use of uterotonics
- 9. number of exchange transfusions and partial exchange transfusions up to 36 weeks gestation

3.4.6 Predefined subgroups

- 1. Gender
- 2. Age: Infants of 26 ⁶ weeks gestation or less or 27 ⁰ weeks gestation or more
- 3. Caesarean Section vs Vaginal birth

4 PARTICIPANT POPULATION

4.1 Participant Population

Male or female pre term babies less than 30 weeks gestational age.

4.2 Inclusion criteria

- mother imminently delivering < 30 weeks of gestation

Page 27 of 81

- informed consent has been received from a parent

4.3 Exclusion criteria

Indication or contraindication to placental transfusion, in view of parent or doctor. Contraindications may include, but are not limited to

- fetal haemolytic disease
- fetal hydrops
- monochorionic twin pregnancies in which there is confirmed twin-twin transfusion syndrome
- major malformations considered incompatible with survival

4.4 Withdrawal criteria

Any family that wishes to withdraw from the trial may do so, without giving a reason and without any change in any other aspect of treatment. Parents of any baby who is withdrawn from the study after randomisation and before or after the intervention is administered will be asked to allow collection of outcome data. Information on hospital outcomes for any baby who is withdrawn after the baby is discharged from hospital will be used in the study.

5 TREATMENT OF PARTICIPANTS

Deferred cord clamping is performed against the background of usual care^{24, 25}. For example, the timing of parenteral administration of uterotonic or the use of plastic wrap to warm the baby would be according to existing local protocols with no changes required for the study.

(a) Immediate cord clamping (< 10 seconds after birth)

• The cord is clamped 6 cm from the umbilicus within ten seconds of delivery of the baby.

(b) Deferred cord clamping

• A birth attendant holds the baby as low as possible below the level of the introitus or placenta for 60 seconds or more, then clamps the cord about 6 cm from the umbilicus.

Variation from the recommended procedures should be undertaken whenever this is judged necessary by the responsible clinician(s) acting in the best interests of the mother or baby. If the baby is *in extremis* or non-vigorous, the attending clinicians may use their discretion in administering the intervention.^{24, 25}

There is concern that palpating the cord may restrict blood flow from placenta to infant. Therefore auscultation is encouraged rather than palpating the cord, subject to the clinician's discretion.

5.1 Compliance

As compliance with this intervention can vary, the following parameters will be recorded and monitored centrally:

- Duration in seconds of deferred cord clamping
- Estimated height in centimetres at which the baby was held in relation to placenta

5.2 Follow-up

To facilitate good follow up, regular contact by phone and/or post will be maintained with the families when the child is 6 months and 12 months to confirm the family's contact details. Sites will send participants birthday cards for each year until follow up has been completed.

Page 28 of 81

6 EFFICACY AND TOLERABILITY

6.1 Assessment of Efficacy

Efficacy will be assessed through routinely collected hospital measures including demographic data, and outcomes such as necrotising enterocolitis and/ or brain injury which are all contained within the medical record.

Children will also have at least 2 follow up assessments: an Ages and Stages questionnaire to assess delay and a short paediatric assessment to determine physical development including incidence of cerebral palsy, eyesight or hearing impairment etc. A random sub-cohort of up to 180 of surviving children will also have a Bayley III Scales of Infant Development assessment, which will be used to calibrate the ASQ results.

6.2 Assessment of Tolerability

Serious adverse events which may be life threatening are common in very preterm infants, however, the proportion of suspected unexpected serious related adverse events (in the opinion of the investigator) is expected to be small.

AN UNEXPECTED SERIOUS ADVERSE EVENT (SAE) is any untoward medical occurrence that is not expected and:

- results in death, or
- is life-threatening (i.e. the subject is at risk of death at the time of the event), or
- requires prolongation of hospitalisation, or
- results in persistent or significant disability or incapacity
- or
 - other important medical events which, in the opinion of the investigator, are likely to become serious if untreated

NOTE: The term "life-threatening" in the definition of "serious" refers to an event in which the baby was at risk of death at the time of the event; it does not refer to an event which hypothetically might have caused death if it were more severe.

An event is considered to be CAUSALLY RELATED if there is a reasonable possibility that the intervention caused the AE i.e. there is evidence to suggest a causal relationship between the intervention and the event.

6.2.1 Reporting of Unexpected Serious Related Adverse Events and Outcome Events The investigator is responsible for reporting all Unexpected Serious Related Adverse Events occurring during the study to the NHMRC Clinical Trials Centre within 1 working day.

Unexpected related SAE reports should be faxed to [contact].

The Trial Management Committee and all other Principal Investigators participating in the study will be informed. The investigator or delegate at each participating institution is responsible for reporting unexpected serious adverse events to their HREC. Serious adverse events will also be reported to the Independent Data and Safety Monitoring Committee.

7 STUDY STRUCTURE

7.1 Trial Management Committee

The NHMRC CTC, in conjunction with the Principal Investigators will appoint a Trial Management Committee (TMC). A Trial Executive Committee (TEC) may be selected from the TMC in order to expedite decision-making and will be led by the Study Chair.

The TMC responsibilities include protocol development, study planning, monitoring of progress and patient safety, review of information from related research and implementation of recommendations

Page 29 of 81

from other study committees and external bodies (e.g. HRECs), and publications. The TMC will be responsible for selection and support of local investigators. The TMC will also monitor rate of recruitment and endpoint occurrence and will advise the SDMC of variations. The TMC will meet twice a year and/ or as required.

The TEC is a subset of the TMC which meets more regularly on key scientific and/or operational issues impacting on study conduct. The TEC will meet at least once every quarter (or as the stage of the trial dictates) as the study progresses.

7.2 Independent Data and Safety Monitoring Committee

An Independent Data and Safety Monitoring Committee (IDSMC) will monitor the progress of all aspects of the study and will ensure that the study meets the highest standards of ethics and patient safety. It will review interim data and other emerging evidence, including relevant RCTs and overviews of RCTs. The IDSMC will advise the TMC if in their view there is proof beyond reasonable doubt of net clinical benefit or harm, for all infants or for a subset of infants, that might reasonably be expected to influence the management of many clinicians. Data on key study outcomes will be monitored every 12 months, or more frequently if requested by the IDSMC, to ensure safety and that the event rates meet protocol projections. If the event rates are lower than expected, the IDSMC can recommend an increase in the study sample size to maintain power.

An interim analysis will be performed after the first 500 patients are recruited and then annually thereafter or as requested by the IDSMC.

The combined endpoint of death and/or major morbidity will be monitored using a modified Haybittle-Peto rule. The IDSMC supports the view that a difference of at least 3 standard deviations (SD) in a major endpoint (or in a combination of major endpoints) that suggested net clinical benefit or harm may be needed to justify recommending that the TMC consider either stopping the study prematurely, monitoring the trial more frequently or modifying the trial design.

7.2.1 Net Clinical Benefit: an important criterion for decision making

Evidence of a significant difference in mortality or in the primary outcome of mortality and morbidity or in mortality and brain injury between the study arms of more than 3 standard deviations would be of major concern and likely to lead to a recommendation to consider stopping recruitment. However, evidence of a significant increase in major morbidity in one arm is not necessarily an indication for early stopping of the trial since this might be balanced by a reduction in deaths or major disability. For example one arm of the study may be associated with an increase in morbidity which is statistically significant, but may also be consistent with a reduction in deaths which is not statistically significant, and with net benefit (not statistically significant) for the other arm. Similarly, evidence of a significant increase in an intermediate measure of adverse outcome, such as intraventricular haemorrhage (IVH) or necrotising enterocolitis (NEC), in one arm of the study is not necessarily an indication to stop early, since this might be balanced by an overall reduction in deaths and/ or major disability in the other arm of the study on follow up. Furthermore, major outcomes on follow up will not be determined until two years after trial entry. In both examples, it may be appropriate to continue the trial and indeed other related trials, until a clearer picture on net clinical benefit was obtained.

8 STATISTICS

8.1 Sample Size

At least 1500 infants and a primary outcome rate in the early clamping group of 41.6% will have 80% power to detect a 24% RRR, allowing for 30% non-compliance at 2p = 0.05. The table below shows other scenarios for larger sample sizes.

able 2. Sample size scenarios using overall study estimate of event rate.							
		Immediate	Delayed				
		Cord	Cord				
		Clamping	Clamping	Overall	Absolute		
Sample Size		%	%	rate %	Reduction%	RRR %	Power
	1500	41.6	31.7	36.65	9.9	24	80

Table 2: Sample size scenarios using overall study estimate of event rate.

Page 30 of 81

1550	41.6	31.8	36.7	9.8	24	80
1600	41.6	32	36.8	9.6	23	80

Infants recruited in some regions will not be included in the analysis for the extended follow-up. Assuming that this will exclude at most 150 infants, the table below gives an estimate for the absolute difference between the interventions that could be detected for a range of sample sizes and event rates for the primary endpoint at that time allowing for 30% non-compliance. Power is set at 80% and the absolute reduction that could be detected is calculated.

Table 3: Long term follow-up scenarios for absolute difference that could be detected for possible sample sizes

Secondary endpoint	Sample Size	Absolute difference	Power
Mortality and major	1350	10% (35% to 25%)	80
disability to 36 months	1400	9.8% (35% to 25.2%)	80
	1450	9.6% (35% to 25.4%)	80
	1350	10.3% (40% to 29.7%)	80
	1400	10.2% (40% to 29.8%)	80
	1450	10% (40% to 30%)	80

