4.1 Projected recruitment and power

Seven new sites will join in 2014. At least 704 more infants from Australia, New Zealand and the United Kingdom are expected in the 22 months to December 2015, yielding >1,320 in which to assess the primary outcome of death or major disability at 3 years. (Figure 2)

The projected total of 1,320 infants gives 80% power to show a decrease of 8.5% in the primary outcome, from 30% to 21.5%, with two tailed significance of p <0.05, based on the current non-adherence rate of 20% (5% in the early clamping group and 15% in the deferred cord clamping group).

An additional 280 infants will be enrolled in sites in Pakistan, India and the United States, yielding a total of 1600 for comparison of in-hospital outcomes. Childhood follow up, the primary outcome for the project, will not be undertaken in these infants because of the increased logistic difficulties in maintaining prolonged contact with families in these countries.

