1.5 Power and Sample Size

Infants recruited into the main APTS study are expected to complete extended follow-up. Assuming that, at most, 150 infants will be lost or not followed to two years, the table below gives an estimate for the absolute difference between the interventions that could be detected for a range of sample sizes and event rates for the primary endpoint allowing for 30% non-compliance. The absolute reduction that could be detected maintaining 80% power is shown.

Table 1: Long term follow-up scenarios for absolute difference that could be detected for possible sample sizes

Secondary endpoint	Sample Size	Absolute difference	Power
Mortality and major disability	1350	10% (35% to 25%)	80
up to 36 months	1400	9.8% (35% to 25.2%)	80
	1450	9.6% (35% to 25.4%)	80
	1350	10.3% (40% to 29.7%)	80
	1400	10.2% (40% to 29.8%)	80
	1450	10% (40% to 30%)	80

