2 STATISTICAL ANALYSIS

The primary analyses will be performed on assigned treatment. As randomisation occurs when birth is imminent, occasionally babies are not born immediately following randomisation. Babies that are stillborn or born after 30 weeks gestation are not to be included in the intention to treat population.

As consent for the babies recruited into the pilot APTS study did not include collection of follow-up data, these pilot babies are not included in the APTS FU study (n=35).

P-values less than 0.05 will be considered statistically significant and there will be no adjustments for multiple comparisons.

Page 4 of 17

Page 68 of 81

APTS FU Statistical Analysis Plan v2.2

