2.2 Follow-up cohort

Table 2: Children with follow-up data available

	Immediate cord clamping	Delayed cord clamping					
Total babies randomised	816	818					
Babies not included in ITT							
 Ineligible babies (born >30 weeks) 	27	27					
• Withdrawn consent (prior to delivery)	2	2					
Stillborn babies	5	5					
Babies included in main study ITT	782	784					
Babies removed because included in the pilot study							
Babies available for the APTS Followup study							
No follow-up obtained	No follow-up obtained						
Partial follow-up obtained, but incomplete							
Data available for primary outcome at 24 months							

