2.6.3.2 Weighted subgroups by treatment adherence approach

Additionally, a weighted average approach, weighting by measures of treatment received will be undertaken, following the same principles used in the APTS main study analyses, while preserving the effect of randomisation. In these planned analyses we propose the following two approaches:

(a) sites which enrolled 50 or more babies will be considered a cluster and sites with less than 50 babies will be amalgamated to make a cluster of over 50 with other sites in the same geographic area;

(b) sites which enrolled 10 or more babies will be considered a cluster and amalgamated into a cluster with sites with less than 10 babies will be amalgamated with others in the same geographic area to form another 'cluster' with 10 or more babies (as shown in Table 9).

August 2020

Page 10 of 17

Page 74 of 81

APTS FU Statistical Analysis Plan v2.2

These clusters are slightly different from those proposed in the main paper as we have fewer patients with the follow-up component of APTS (1531 vs 1566), and also fewer with complete data at 2 years. Analysis (b), in which sites of 10 or more babies will be considered a 'cluster' as per Table 9, will allow us to assess the effect of placing less emphasis on the arbitrary grouping of sites by geographical location in analysis (a).

The main measure to be used to estimate treatment adherence will be the mean difference in clamp time (in seconds) between the ICC and DCC arms. Additional measures to be investigated include:

- mean clamp time in seconds in the DCC arm only
- proportion of compliant babies, where compliant is <10 seconds and not milked versus >=60 seconds and not milked
- proportion of babies who are compliant in the DCC arm only (>=60seconds and not milked)

For each measure of treatment adherence, the average for each treatment in each cluster will be calculated. For some measures, the difference between the two treatments will be calculated while for others, the measure of treatment received in the delayed clamping arm alone will be used. This value will then be used to rank the (a) 15 and (b) 22 clusters (as below in Table 9) for increasing adherence to protocol. These clusters in (a) and (b) will be grouped into 3 sets according to adherence to protocol, i.e. (a) 5 'low', 5 'medium' and 5 'good' adherence to protocol treatment (total 15 clusters) or (b) 7 'low', 8 'medium' and 7 'good' adherence to protocol treatment (total 22 clusters).

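### Protocol V4.0 keeps some regions out of the follow-up analysis and SAP v2.2 does not; if any region was not followed, its deaths would count in the primary outcome and its survivors would not

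*Supplement*

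**What the plan says.** **Protocol V4.0, 8.1 Sample Size.** The text before Table 3 states: "Infants recruited in some regions will not be included in the analysis for the extended follow-up". It continues: "Assuming that this will exclude at most 150 infants", and the table gives detectable differences for 1350, 1400 and 1450 infants. The summary of changes records no formal amendment after V4.0.

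**SAP v2.2, 1.5 Power and Sample Size.** The corresponding paragraph opens: "Infants recruited into the main APTS study are expected to complete extended follow-up". The 150 reappear with another meaning: "Assuming that, at most, 150 infants will be lost or not followed to two years". The table beneath has the same sample sizes and differences.

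**SAP v2.2, sections 2 and 2.2.** Stillborn babies, babies born after 30 weeks and consent withdrawn before delivery are removed to reach the row "Babies included in main study ITT" (782 and 784). For the follow-up study the only further group removed is the pilot: "these pilot babies are not included in the APTS FU study (n=35").

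**SAP v2.2, 2.6.3.2 and Table 9.** The text speaks of "fewer patients with the follow-up component of APTS (1531 vs 1566"). Table 9 lists Pakistan, France and North America among the clusters.

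**SAP v2.2, 2.5.** Death alone meets the primary outcome. A child counts as alive at 24 months only if known to be alive at 21 months corrected age or later. A survivor without the needed disability information is missing from the primary analysis.

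**Follow-up funding application (2014), 4.1.** It names Pakistan, India and the United States and says: "Childhood follow up, the primary outcome for the project, will not be undertaken in these infants".

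**The concern.** The latest protocol and the latest SAP disagree about who belongs to the primary analysis of the follow-up study. One leaves a group out by region; the other includes every main-study infant except the pilot babies. In the SAP, a planned exclusion has become attrition.

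This matters because the primary outcome is a composite with unequal ascertainment. In-hospital deaths are known from the main study without any extended follow-up, whereas classifying a survivor needs later contact and assessment. If a site did not take part in extended follow-up but stays in the SAP cohort, whether its infants are analysed depends on their outcome: deaths enter as events, survivors drop out. Such a site would show a 100% event rate in both arms. The reported rates would be too high, and the relative risk would mix death or disability in followed regions with death only elsewhere. The binary comparison of death at 24 months would have the same difficulty, since its survivors also need contact at 21 months or later.

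**Working it through.** **1. Reproduce the SAP cohort.** Main-study ITT: 782 + 784 = 1566 (SAP Table 2). Less 35 pilot babies: 1566 - 35 = 1531, exactly the figure in SAP 2.6.3.2. Infants removed for region: none.

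**2. Reproduce the protocol's follow-up table.** 1500 - 150 = 1350, 1550 - 150 = 1400 and 1600 - 150 = 1450, so in the protocol the 150 are the regional exclusion. With a two-sided 5% test, 1:1 allocation and 80% power, splitting the 30% non-compliance equally between arms gives required totals of 1344, 1402 and 1464 (35% control rate) and 1370, 1398 and 1456 (40%), against the printed 1350, 1400 and 1450. The table reproduces closely; only the meaning of the 150 differs between the documents.

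**3. Apply the SAP's outcome rules to an unfollowed region.** Inputs:
- Unfollowed infants n = 150, the protocol's upper limit, 75 per arm.
- Followed infants 1531 - 150 = 1381, or F = 690.5 per arm.
- Event rates in followed regions 35% (immediate) and 28% (delayed), RR 0.80. The 35% is one of the control rates in the protocol's table; the 28% is assumed.
- Regional mortality m = 5% to 30%, assumed, because V4.0 and the SAP give no rate for such regions.

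With d = 75m deaths per arm, equal in both arms, the observed rate in an arm is (F × p + d)/(F + d).

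Example, m = 10%: d = 7.5.
- Immediate: (241.675 + 7.5)/(690.5 + 7.5) = 249.175/698 = 35.7%.
- Delayed: (193.34 + 7.5)/698 = 28.8%.
- RR = 0.806.

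| m | Deaths entering | Survivors missing | Immediate | Delayed | RR |
|---|---|---|---|---|---|
| 5% | 7.5 | 142.5 | 35.4% | 28.4% | 0.803 |
| 10% | 15 | 135 | 35.7% | 28.8% | 0.806 |
| 15% | 22.5 | 127.5 | 36.0% | 29.2% | 0.809 |
| 20% | 30 | 120 | 36.4% | 29.5% | 0.812 |
| 30% | 45 | 105 | 37.1% | 30.3% | 0.817 |

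**4. Unequal deaths.** If regional deaths in the delayed arm are 0.7 times those in the immediate arm, the delayed rate is (F × p + 0.7d)/(F + 0.7d). For a true RR of 0.80 the result stays at 0.799 to 0.800 over the same range of m. For a true RR of 1 it becomes 0.997 (m = 5%) to 0.984 (m = 30%).

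**5. Compare with sampling error.** For 690.5 per arm and rates of 35% and 28%, var(ln RR) = 0.65/241.675 + 0.72/193.34 = 0.00641, SE 0.080. The 95% interval around 0.80 is about 0.68 to 0.94, ignoring clustering of multiple births.

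**6. Does anything else in the SAP remove the problem?** Tables 2 and 6 would show how many infants lack follow-up or a component, but do not change who is analysed. Multiple imputation (2.6.4) is a sensitivity analysis, and its listed covariates include neither site nor region, so survivors in an unfollowed region would be filled in from children elsewhere.

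**The case against.** The strongest reply is that the SAP replaced the regional exclusion deliberately. It is dated August 2020, four years after V4.0. It reuses the protocol's paragraph and table but swaps the regional sentence for one expecting main-study infants to complete follow-up, and it keeps overseas sites in Table 9. Read alone, the SAP is coherent: all regions are in, and the stale sentence is the protocol's. Removing sites that were in fact followed would then discard valid randomised data. This is a serious possibility, and the remedy has to allow for it. It does not settle the matter: the account of SAP changes in the supplement describes the new outcome but not a change of population, and SAP 2.5.2 refers to babies eligible for follow-up without defining eligibility by site.

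It is also fair that the bias is small beside the sampling error, and that deaths are easier to ascertain than disability-free survival in any infant lost to follow-up. The regional case differs in being foreseeable by site and removable by a rule that does not look at the outcome, as the SAP already does for the pilot babies.

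Two stronger readings are tempting. A reader might infer that unfollowed regions do enter through deaths alone; no section says any region was unfollowed when the SAP was written. A reader might also take the 280 infants planned for three countries in the 2014 application as the size of the group. That forecast precedes V4.0, which caps the exclusion at 150, and its countries do not match Table 9, which lists no Indian site and includes a French one.

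**Conclusion.** The conflict between Protocol V4.0 8.1 and SAP v2.2 is real and leaves the primary population of the follow-up study undefined for up to 150 infants. The outcome-dependent inclusion is conditional: it follows from the SAP's rules only if some region was not followed, which the documents neither establish nor exclude. In that case, with 150 infants and assumed mortality of 5% to 30%, observed event rates rise by about 0.4 to 2 points and an RR of 0.80 moves by at most 0.017, towards 1 if deaths are equal by arm. With fewer deaths in the delayed arm (ratio 0.7) it hardly moves, and a true null shifts by up to 0.016 below 1. The case for acting is a clear population and honest event rates at little cost, rather than a large bias in the treatment effect.

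**What to change.** Before unblinding, state which sites took part in extended follow-up and bring the two documents into line.

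- **If some sites did not take part:** add a row to SAP Table 2, above the row giving the follow-up cohort, for infants at those sites by arm. Exclude them by randomising site, deaths and survivors alike, from the 24-month composite, its imputation and the adherence clusters in Table 9. Say whether the binary death outcome uses the same cohort.
- **If all sites took part:** correct Protocol 8.1, keep every site, and state in the SAP that the regional exclusion no longer applies.

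The cost is wording and at most one table row, with no new data. Exclusion would lose a few events: at the limit the cohort falls to 1531 - 150 = 1381. With 80% power and all the 30% non-compliance assigned to one arm, the detectable difference goes from 9.5 to 10.0 points at a 35% control rate and from 9.8 to 10.35 points at 40%.
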